9.3.2.2.2 Infant Outcomes

- Rate and pattern of minor structural **birth** defects where a minor structural **birth** defect is defined as a structural anomaly (itemized on the study examination form) which has neither cosmetic nor functional significance to the child, and a pattern is defined as the same 3 or more minor structural **birth** defects in 2 or more children (see [Appendix A](#), 04.E. Dymorphology Exam Form). Due to the large variability in the sensitivity and specificity of identification of minor defects, in this study, minor defects are tabulated only in those infants who receive the study-related physical examination. This approach of assessment for clusters is based on prior studies that suggest 3 or more minor malformations is a meaningful cut point ([Leppig et al, 1987](#); [Méhes et al, 1973](#); [Marden et al, 1964](#)).
- Rate of small for gestational age where small for gestational age is defined as birth size (weight, length, or head circumference) \leq 10th centile for sex and gestational age using standard pediatric CDC growth curves for full term or preterm infants ([NCHS, 2000](#); [Olsen et al, 2010](#)).
- Rate of postnatal growth deficiency where postnatal growth deficiency is defined as postnatal size (weight, length, or head circumference) \leq 10th centile for sex and age using standard pediatric growth curves, and adjusted for postnatal age for premature infants if the postnatal measurement is obtained at less than 1 year of age.
- Rate of postnatal serious infections (see [Appendix D](#)) and hospitalizations as assessed throughout the 5-year postnatal follow-up period. Pediatric records will be requested after delivery and then on an annual basis with specific requests for documentation of serious infections and hospitalizations
- Rate of infant reactions to scheduled vaccinations as assessed throughout the 5-year postnatal follow-up period. Pediatric records and a questionnaire regarding vaccine administration according to recommended schedule and any vaccine-related adverse events will be obtained on an annual basis (see [Appendix A](#), 08.12. Vaccine Information Form).
- Infant response to IgG-tetanus antibody as a biological marker to evaluate humoral immune response. To be performed via a heel stick **or venipuncture** and standardized assay test between 6-12 months of age in a subset of infants in each of the study groups, conditional on the consent of the mother.

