9.4.4 Medical Records, Pediatric Evaluations

Upon completion of the outcome interview, each woman will be mailed a packet containing medical records release forms for the delivery hospital, obstetrician (**if the release form has not been received**), pediatrician, internist, cardiologist or other specialty physician if applicable (see [Appendix A](#), Form 09.J. Sample OB Medical Records Release Form). For women whose pregnancies have ended in spontaneous or elective abortion or stillbirth, records release forms will be mailed for the specialty physician's evaluation, if applicable, and if prenatal diagnosis, pathology or autopsy reports are available. Each woman will be asked to sign the forms and to return them along with the **patient** exposure diary. Specific information on maternal cholesterol levels obtained prior to and during pregnancy will be requested for women in the Evolocumab-Exposed group and Comparison Group I.

Upon receipt of the signed medical records release forms, a standard physical evaluation form (see [Appendix A](#), 06.H. Birth Info and Private Pediatrician Form) will be mailed to each pediatrician or other physician responsible for the care of each live born infant. This form includes information on infant size at the time of the latest examination and questions about postnatal complications and congenital anomalies. After delivery, at 1 year of age, and annually thereafter until the child's fifth birthday, a medical records release form for the pediatrician or health care provider caring for the child will be sent to the mother for signature. The signed form along with a standard questionnaire about infant/child growth, congenital malformations, serious infections (see [Appendix D](#) for list of conditions qualifying as serious infection), hospitalizations, and adverse reactions to vaccinations administered is sent to the health care provider (see [Appendix A](#), 07.I. Pediatric One Year Follow-up Form, and 08.I2. Vaccine Information Form).

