For the primary outcome, the study is powered to detect that the Evolocumab-Exposed group has a 3.8-fold (or greater) risk of all major **structural** birth defects combined relative to the risk in the primary comparison group. This level of risk for teratogenicity is below that observed for other, but not all, agents deemed teratogenic. Importantly, known human teratogens tend to be associated with increased risks for specific patterns of birth defects and are not associated with increased risks for any and all major **structural birth** defects. For this reason, the analysis of the primary outcome, combined with evidence of a cluster or pattern of defects, provides the best ability for evaluation of teratogenic risk.

Table 3. Sample Size and Power for a Specified Effect Size Based on Minimal Sample Size^a

Outcome	N in Cohort 1	N in Cohort 2 or 3	Baseline Rate	RR	Power ^b
Major structural birth defects ^c	71	142	4% ^d	3.8	84%
Specific pattern of 3 or more minor structural birth defects	60	120	1% ^e	10.0	71% ^f
Spontaneous abortion/stillbirth	71	142	10% ^g	2.5	88%
Preterm delivery	60	120	9% ^h	2.8	85%
SGA	60	120	10% ⁱ	2.6	80%
Small for age (postnatal growth deficiency)	46	108	10%	2.8	82%
Neurodevelopmental outcomes (Phase II)	40	40	--	0.5 SD ^j	80%
Inadequate immune response (via IgG tetanus antibody status)	60	120 ^k	20% ^l	2	82%

Definitions: Ig = immunoglobulin; RR = relative risk; SGA = small for gestational age.

^a Software used to calculate power and effect size: OpenEpi v3 (Dean et al, 2015).

^b Based on Fisher's Exact Test or chi-square, two-tailed, alpha 0.05, except for specific pattern of 3 or more minor anomalies as noted below.

^c Primary endpoint.

^d Baseline rate in comparison group based on 4.1% in statin exposed (Winterfeld et al, 2013).

^e Baseline rate in comparison group expected to be 0-1% based on no evidence of a pattern.

^f Based on one-tailed Fisher's Exact Test, alpha 0.05.

^g Baseline rate based on 13.6% in statin exposed (Winterfeld et al, 2013) and 4.4% (Chambers et al, 2013) (rate influenced by gestational time of enrollment).

^h Baseline rate based on 16.1% (Winterfeld et al, 2013) and 6.2% (Toleikyte et al, 2011).

ⁱ Baseline rate based on 5.0% for low birth weight defined as < 5th centile which translates to 10% for SGA defined as < 10th centile (Toleikyte et al, 2011).

^j Minimum detectable difference calculated for neurodevelopmental outcomes as a continuous variable (instead of RR for categorical variables).

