9.7.2 Planned Method of Analysis

9.7.2.1 General Considerations

The analysis of the cohort dataset will be hypothesis testing. The analysis of the exposed case series will be descriptive only. Significance testing at the alpha level of 0.05 will be utilized for the cohort analysis as well as 95% confidence intervals for rate ratios. Due to the small sample size, no adjustment for multiple testing is planned.

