9.7.2.5.2 Secondary Analysis

The following will comprise the secondary analyses:

1. Comparison of all secondary outcomes between the Specific Evolocumab-Exposed cohort and Comparison Group I
2. Comparison of the primary and all secondary outcomes between the Specific Evolocumab-Exposed cohort and Comparison Group II

The comparison of the prevalence of the total proportion of major structural **birth** defects between the Specific Evolocumab-Exposed cohort and Comparison Group II will be among all live births and, separately, among all pregnancies excluding those lost to follow-up. The comparison of the prevalence of ≥ 3 minor malformations between the Specific Evolocumab-Exposed cohort and each of the 2 comparison groups will be among children who receive the dysmorphological examination. The comparison of IgG-tetanus antibody status (test negative or indeterminate vs test positive) by group (Exposed, Comparison Group I, Comparison Group II) among those in the biological sample sub-study.

In each cohort we will separately calculate the proportion of all pregnancies ending in live birth, spontaneous abortion, stillbirth, elective termination, and lost to follow-up; crude comparisons will be made between cohorts.

The evaluation for a pattern of minor structural **birth** defects will be conducted using the following steps:

1. A comparison among groups of the proportion of infants with any 3 or more minor structural **birth** defects will be made without regard to pattern
2. Among infants with 3 or more minor **structural birth** defects, the Evolocumab-Exposed group will be examined for evidence of a specific pattern of 3 or more defects in any 2 or more children. If such a pattern is identified, Comparison Groups I and II will be evaluated for any evidence of the same pattern.

In each cohort among all live born infants we will separately calculate the proportion of premature delivery, small for gestational age on weight, length or head circumference, and rates of serious infections, hospitalizations, adverse vaccine reactions, and adverse neurodevelopmental outcomes; crude comparisons will be made between cohorts.

Mean birth weight, length and head circumference for full-term live born infants will be compared between cohorts. Postnatal growth parameters will be compared using the proportion of infants ≤ 10 th centile for sex and age with respect to weight, height, or head circumference.

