Among the subset of live born infants who participate in the IgG-tetanus antibody assessment at 6-12 months of age, adequacy of immune response will be compared between groups.

Among mothers who give birth to live born infants, the proportion who breastfeed in the first 6 weeks post-delivery will be compared; also among those who breastfeed, the proportion who breastfed exclusively during the first 2 weeks of life.

At the end of the study or as deemed appropriate in consultation with the Scientific Advisory Board, unadjusted and adjusted comparisons between cohorts will be made. Potential confounders will be examined, and adjusted estimates of exposure effects (along with 95% confidence intervals) will be made using Cox proportional hazards, logistic regression, or linear regression techniques as appropriate. Propensity score methods will be considered for adjusted analyses when more than 1 confounder is identified.

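### Postnatal growth is compared only as a rate at the 10th centile; a z-score comparison should stand beside it, and birth size should not be compared in full-term infants only

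*Protocol*

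**What the plan says.** Protocol 9.3.2.2.2 sets the outcome as a rate: "postnatal growth deficiency is defined as postnatal size (weight, length, or head circumference") at or below the 10th centile for sex and age, with an age correction for premature infants measured before 1 year. Section 9.7.2.5.2 fixes the comparison in the same form: "Postnatal growth parameters will be compared using the proportion of infants" at or below that centile. The sentence before it treats size at birth differently: "Mean birth weight, length and head circumference for full-term live born infants will be compared between cohorts".

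The underlying measurements are continuous. Section 9.4.4 says of the form sent to the child's physician: "This form includes information on infant size at the time of the latest examination".

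Table 3 in 9.5 powers postnatal growth as a binary outcome. The row "Small for age (postnatal growth deficiency") gives 46 exposed and 108 comparison infants, a 10% baseline, RR 2.8 and 82% power, by Fisher's exact test or "chi-square, two-tailed, alpha 0.05". The Phase II neurodevelopment row of the same table is expressed in SD units. Linear regression appears in 9.7.2.5.2 only in a general sentence on adjusted estimates, "using Cox proportional hazards, logistic regression, or linear regression techniques as appropriate", and is not tied to postnatal growth.

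**The concern.** Cutting a measured quantity at one point discards how far each infant lies from the cut. With 46 exposed infants, that matters. Embryo-fetal growth and development is among the safety signals in the FDA requirement described in section 7, and 9.9 concedes that sample size limits power. If exposure lowered growth moderately across all infants, a non-significant difference in proportions could be taken as reassurance when the same data, analysed on their own scale, would have shown the effect.

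Size at birth has a related weakness. Means are compared, but only in full-term infants. Term status arises after exposure. If exposure affects gestation, restricting to term infants conditions on a consequence of exposure and drops the infants most likely to be affected.

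**Working it through.** **Inputs (Table 3 and its footnotes).** Postnatal growth: n = 46 and 108, 10% baseline, RR 2.8, hence 28% exposed; two-sided alpha 0.05; Fisher or chi-square; printed power 82%. SGA: n = 60 and 120, 10% baseline, RR 2.6, hence 26%.

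**1. The protocol's own figure.** Pooled normal formula:
- pooled proportion = (46 × 0.28 + 108 × 0.10)/154 = 0.1538
- SE under the null = √[0.1538 × 0.8462 × (1/46 + 1/108)] = 0.0635
- SE under the alternative = √[0.28 × 0.72/46 + 0.10 × 0.90/108] = 0.0722
- power = Φ[(0.18 − 1.96 × 0.0635)/0.0722] = Φ(0.77) = 77.9%

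Summing the two binomial distributions over all tables that reject gives 79.1% for chi-square and 73.6% for Fisher. The printed 82% is not reproduced by either test named in the footnote. The comparison below therefore starts from 73.6–79.1%; measured from the printed 82%, the gain would be about 16 points.

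**2. The same effect on the z-score scale.** Assume normal z-scores, equal SD and a shift of every exposed infant.
- shift = Φ⁻¹(0.28) − Φ⁻¹(0.10) = −0.583 + 1.282 = 0.70 SD
- noncentrality = 0.699/√(1/46 + 1/108) = 0.699/0.1761 = 3.97, with 152 df
- t-test power = 97.6%, a gain of about 18 points over chi-square and 24 over Fisher

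**3. A smaller shift, 0.5 SD.**
- exposed proportion = Φ(−1.282 + 0.5) = 21.7%
- power for the proportion: 42% (Fisher), 50% (chi-square)
- t-test: noncentrality 0.5/0.1761 = 2.84, power 81%

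**4. If the cut means any of the three measures.** The correlation between measures is not in the protocol; 0.5 to 0.7 is assumed. By simulation with each measure cut at its own 10th centile, a 0.5 SD shift in all three gives 64–70% for chi-square. One z-score still has 81%, so the gap is about 11–17 points.

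**5. If only some infants are affected.** Hold the exposed rate at 28% and let a fraction π shift by d SD: π = 0.18/[Φ(−1.282 + d) − 0.10].

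| d (SD) | π | t-test power (lower figure unequal-variance, higher pooled) |
|---|---|---|
| 1.0 | 0.18/0.289 = 62% | about 91% (normal approximation) |
| 1.5 | 0.18/0.486 = 37% | 76–81% |
| 2.0 | 0.18/0.664 = 27% | 69–76% |

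The proportion has 73.6–79.1% in every row, so by the last two rows the advantage is gone or reversed against chi-square.

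**6. Size at birth.**
- SGA shift = Φ⁻¹(0.26) − Φ⁻¹(0.10) = 0.64 SD
- power: 74% (Fisher) to 79% (chi-square) for the proportion, 98% for a t-test on z-scores under the assumptions of step 2
- infants outside a full-term comparison: 9% at the Table 3 preterm baseline, 9% × 2.8 = 25% in the exposed cohort at the Table 3 RR

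**7. Detectable shift at 80% power** (normal formula, (1.96 + 0.842) × √(1/n₁ + 1/n₂)).
- postnatal growth: 2.802 × 0.1761 = 0.49 SD (0.50 by the t distribution)
- birth size: 2.802 × 0.1581 = 0.44 SD

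**The case against.** The strongest reply is that the analysis answers the question asked. The outcome is a rate, the secondary objective in 8.2 is to estimate rates, and the FDA requirement is framed as incidence rates. A difference in mean z-score is another estimand, not a sharper test of the same one. This stands, and it rules out dropping or demoting the comparison of proportions.

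Second, a reader might infer that the cut costs 18 to 24 points of power whatever happens. The documents do not support that. The figure needs a shift of the whole distribution, which the protocol neither states nor excludes, and step 5 shows that it can vanish. Nor does a moderate shift simply go undetected: on the any-of-three reading, chi-square has 64–70% at 0.5 SD.

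Third, a reader might infer that the protocol forbids a continuous analysis. It does not. Linear regression is listed in general terms, and a supplementary model may sit in the SAP, which is not among the documents examined here. But 9.7.2.5.2 does fix how postnatal growth is compared, and a general reference to regression does not assign a z-score analysis to it.

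Fourth, birth size already has a continuous comparison that keeps about 91% of infants at the baseline preterm rate, and preterm delivery is compared as its own outcome. So the loss at birth is smaller than the SGA figures alone suggest. What remains is the restriction on a post-exposure variable.

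**Conclusion.** The point holds as a case for adding an analysis. Under a whole-distribution shift with normal z-scores and equal SD, comparing z-scores raises power from 74–79% to about 98% at the Table 3 effect, and from 42–50% (single measure) or 64–70% (any of three, assumed correlation 0.5–0.7, chi-square) to 81% at 0.5 SD. If the same 28% rate arises because roughly a third or fewer of the infants are strongly affected, the proportion does as well or better. Neither analysis dominates, and the protocol has no basis for knowing which pattern would apply. Reporting both covers both. Restricting birth-size means to term infants is a separate, smaller weakness that gestational-age z-scores remove. These are secondary outcomes; the primary analysis is untouched.

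**What to change.** In 9.7.2.5.2:
- Keep the between-cohort comparison of the proportion at or below the 10th centile as the defined postnatal growth outcome.
- Add a linear-regression comparison of sex- and age-specific z-scores for weight, length and head circumference, with age corrected for prematurity when the measurement is before 1 year.
- At birth, replace the full-term-only means by gestational-age- and sex-specific z-scores in all singleton live births.

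In 9.5, state the detectable SD difference beside the growth rows of Table 3: about 0.50 SD for postnatal size and 0.44 SD for birth size at 80% power with the stated numbers.

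The change needs no new data, visits or participants: the measurements, the growth references and linear regression are already in the protocol. It does add a few secondary tests. Section 9.7.2.1 says "Significance testing at the alpha level of 0.05 will be utilized for the cohort analysis" and plans no multiplicity adjustment, so the chance of a false positive rises somewhat. A z-score difference is also less familiar to clinicians than a rate, which is a further reason to keep the rate.

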9.7.2.6 Sensitivity Analysis

Because early prenatal diagnostic testing is prevalent in the US and increasingly performed prior to the second trimester, it is not feasible to exclude all pregnancies with prior prenatal testing from the analysis. Thus, the Registry will include pregnancies that are enrolled prior to outcome but after a prenatal test has been performed, as long as the test does not indicate a major structural **birth** defect. Because of the possibility that this practice could potentially bias the results, analyses for the primary outcome of major **structural** birth defects will be stratified by use of prenatal testing and on gestational timing of enrollment (prior to prenatal testing).

The intention of the primary endpoint is to analyze pregnancies with evolocumab exposure occurring in the first trimester. In the event that there are exposures in the second and third trimester, sub-analyses will be conducted based on length of exposure and timing of exposure, when feasible.

Outcomes that can be adjudicated as not associated with drug exposure will not be included in the primary analysis. Those outcomes, such as chromosomal and genetic abnormalities, that cannot be adjudicated as not associated with drug exposure will be analyzed in the primary analysis as well as in multiple sensitivity analyses that will be designed to address the specific outcomes observed and are impractical to fully pre-specify. However, they will be in keeping with other ongoing studies, advice received from experts, and current and evolving FDA registry guidance.

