9.2.3 Subject Eligibility

9.2.3.1 Inclusion Criteria

(1) Specific Evolocumab-Exposed Cohort

- Qualified subjects will be currently pregnant women (maternal report validated by medical records) diagnosed with ASCVD, or hypercholesterolemia associated with FH who have been exposed to evolocumab for any number of days, at any dose, and at any time from the first day of the LMP up to and including the end of pregnancy. If the date of the LMP is unclear, or if a first-trimester ultrasound has been done and the estimated date of conception is more than 1 week discrepant from the menstrual period calculation, the first-trimester ultrasound-derived date will be used to calculate a date for LMP and conception.
- Qualified subjects will agree to the conditions and requirements of the study including the interview schedule, release of medical records, the physical examination of live born infants, and 5 years of follow-up.

(2) Comparison Group I

- Qualified subjects will be currently pregnant women (maternal report validated by medical records) diagnosed with ASCVD, or hypercholesterolemia associated with FH but who were not exposed to evolocumab during pregnancy or any time within 90 days prior to the first day of the LMP.
- Qualified subjects will agree to the conditions and requirements of the study including the interview schedule, release of medical records, the physical examination of live born infants, and 5 years of follow-up.

(3) Comparison Group II

- Qualified subjects will be currently pregnant women not diagnosed with ASCVD, or hypercholesterolemia associated with FH, who have not been exposed to evolocumab during pregnancy or any time within 90 days prior to the first day of the LMP, and who have no exposure to any known human teratogens as determined by the OTIS Research Center.
- Qualified subjects will agree to the conditions and requirements of the study including the interview schedule, release of medical records, the physical examination of live born infants, and 5 years of follow-up.

(4) General Evolocumab-Exposed Case Series

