9.3 Variables

9.3.1 Exposure Assessment

The period defining exposure to evolocumab during pregnancy will be any number of days, at any dose, and at any time from the first day of the LMP up to and including the end of pregnancy. Pregnancy will be assessed via maternal report validated by medical records. If the date of the LMP is unclear, or if a first-trimester ultrasound has been done and the estimated date of conception is more than 1 week discrepant from the menstrual period calculation, the first-trimester ultrasound-derived date will be used to calculate a date for LMP and conception.

The period defining non-exposure to evolocumab during pregnancy will be any time within 90 days prior to the first day of the LMP.

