9.7.2.4.1 Description of Study Enrollment

Outcome	Analysis Subset
Major Structural Birth Defect Among Live Births	All pregnancies ending in at least 1 live born infant
Major Structural Birth Defects Among All Pregnancies Excluding Lost to Follow-Up	All pregnancies excluding lost to follow-up
Spontaneous Abortion	Pregnancies enrolled prior to 20 weeks' gestation
Stillbirth	Pregnancies enrolled excluding lost to follow-up
Preterm Delivery	Pregnancies enrolled prior to 37 completed weeks' gestation, excluding pregnancies ending in twin or higher order multiple births
Minor Structural Birth Defects	Live born infants who have received the dysmorphology examination
Small for Gestational Age Infants	Live born infants excluding twin or higher order multiple births
Breastfeeding	Pregnancies ending in at least 1 live born infant
Postnatal Growth	Live born infants followed up to 1 year postpartum, excluding twin or higher order multiple births
Serious or Opportunistic Infections	Live born infants followed up to 1 year postpartum
Immune Function	Live born infants who received the tetanus titer testing
Response to vaccines	Live born infants who received at least one vaccine
Neurodevelopment	Live born infants for whom developmental screening questionnaires were completed or face-to-face testing was completed

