9.7.2.5 Analysis of the Primary, Secondary, and Exploratory Endpoint(s)

9.7.2.5.1 Primary Analysis

Comparison of the primary outcome between the Specific Evolocumab-Exposed cohort and Comparison Group I will serve as the primary analysis.

Comparison of the prevalence of major structural **birth** defects between the Specific Evolocumab-Exposed cohort and Comparison Group I will be among all live births and, separately, among all pregnancies excluding those lost to follow-up.

Outcomes that are adjudicated as not associated with drug exposure will be excluded from the primary analysis, but included in a sensitivity analysis ([Section 9.7.2.6](#)).

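### The protocol says the primary endpoint is meant for first-trimester exposure, but neither the primary analysis nor the analysis-subset table restricts exposure by timing.

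*Protocol*

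**What the plan says.** Four parts of the protocol define who counts as exposed without a limit on timing.

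- Section 9.2.3.1 (Inclusion Criteria) admits to the Specific Evolocumab-Exposed Cohort women exposed "at any time from the first day of the LMP up to and including the end of pregnancy".
- Section 9.3.1 (Exposure Assessment) repeats this as the exposure variable: "The period defining exposure to evolocumab during pregnancy will be any number of days, at any dose, and at any time" in that same window.
- Section 9.7.2.5.1 (Primary Analysis) then reads: "Comparison of the primary outcome between the Specific Evolocumab-Exposed cohort and Comparison Group I will serve as the primary analysis". It runs the comparison among live births and, separately, among all pregnancies with follow-up.
- The table in Section 9.7.2.4.1 gives the subsets for major structural defects as pregnancies with a live birth and "All Pregnancies Excluding Lost to Follow-Up". Neither row mentions when exposure occurred.

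One part says something narrower. Section 9.7.2.6 (Sensitivity Analysis) states "The intention of the primary endpoint is to analyze pregnancies with evolocumab exposure occurring in the first trimester". For exposures in the second and third trimester it adds that "sub-analyses will be conducted based on length of exposure and timing of exposure, when feasible". Section 9.7.2.6.1 repeats the plan for subgroups by timing and length of exposure, also as feasible.

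**The concern.** Two analysts could build different exposed sets for the headline result, and each could cite the protocol. One would take the whole cohort from Sections 9.2.3.1 and 9.7.2.5.1. The other would keep only first-trimester exposures, following Section 9.7.2.6.

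The choice matters because Section 9.7.2.6 treats the first trimester as the window of interest for this endpoint. A woman first exposed later adds to the exposed denominator, but on that reasoning adds no drug-related defects. Including her moves the relative risk toward 1. In a registry set up to look for teratogenicity, that is the direction of false reassurance. Section 9.9 already describes the sample as modest and power as limited, so there is little to spare.

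The set should also be fixed before outcomes are compared. Otherwise the headline population is chosen with results in view.

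**Working it through.** **Inputs from the protocol** (Section 9.5 and Table 3): 71 analysable exposed pregnancies, 142 in the comparison group, 4% baseline rate, RR 3.8 (so 0.04 × 3.8 = 15.2% in the exposed), and a test described as Fisher's exact or "chi-square, two-tailed, alpha 0.05".

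**Inputs assumed**, because the protocol gives neither: a share *f* of the exposed cohort is exposed only after the first trimester, and those women have RR 1 for structural defects.

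**The plan's own figure first.** Table 3 gives 84% power for this outcome. From the stated inputs I get 76.4% with the exact two-sided Fisher test, 78.4% with the pooled normal formula and 79.7% for the exact power of the uncorrected chi-square. The 80% in the abstract is consistent with the upper end of that range; 84% is not reproduced by any of the three. That is a separate matter. Here the reference value is the Fisher figure of 76.4% at *f* = 0.

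**Dilution.** The expected relative risk in the any-time cohort is

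RR(*f*) = 3.8(1 − *f*) + *f*, with exposed risk 0.04 × RR(*f*).

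- *f* = 2%: 3.8 × 0.98 + 0.02 = 3.744, risk 14.98%
- *f* = 5%: 3.8 × 0.95 + 0.05 = 3.66, risk 14.64%
- *f* = 10%: 3.8 × 0.90 + 0.10 = 3.52, risk 14.08%
- *f* = 20%: 3.8 × 0.80 + 0.20 = 3.24, risk 12.96%

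**Restriction.** Keeping only first-trimester exposures leaves the risk at 15.2% but cuts the exposed number to 71(1 − *f*), rounded down: 69, 67, 63 and 56.

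**Exact two-sided Fisher power, alpha 0.05, 142 comparison pregnancies:**

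| Late-only share *f* | RR, any-time | Power, any-time (n = 71) | Power, first-trimester only | Gain from restriction |
|---|---|---|---|---|
| 0% | 3.80 | 76.4% | 76.4% (n = 71) | 0 |
| 2% | 3.74 | 75.1% | 75.1% (n = 69) | 0 |
| 5% | 3.66 | 73.0% | 75.3% (n = 67) | 2.3 points |
| 10% | 3.52 | 69.3% | 74.2% (n = 63) | 4.9 points |
| 20% | 3.24 | 61.1% | 69.5% (n = 56) | 8.4 points |

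Exact power does not move smoothly with sample size, so rounding matters a little. With 64 instead of 63 the 10% figure is 73.9%, and with 57 instead of 56 the 20% figure is 71.1%. The pooled normal formula, with n rounded to the nearest whole number (67, 64, 57), gives the same pattern: 75.5% against 77.3% at 5%, 72.4% against 76.4% at 10%, and 65.3% against 74.1% at 20%.

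**The case against.** The strongest reply is that the passages can be read together. The inclusion criteria define a cohort that serves many outcomes, and some of these need later exposure: Section 9.4.5.2 says brain development may be vulnerable beyond the first trimester. Section 9.7.2.5.1 names the groups compared without saying that timing is ignored. Section 9.7.2.6 then narrows this one endpoint. On that reading the restriction is already intended.

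This stands in part. A reader might infer that the protocol has settled on an any-time primary analysis; it has not, because Section 9.7.2.6 points the other way. But that section states an intention, under a sensitivity heading, and neither the primary analysis section nor the subset table applies it. The inconsistency is unresolved.

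The second reply is that late-only exposure will be rare. Section 9.5 expects enrolment at an average of 7 to 10 weeks, and a woman who is already exposed when she enrols that early is a first-trimester exposure. Section 9.9 expects some exposures in unintended pregnancies, and Section 9.7.2.6 treats later exposure as a contingency. These points do not cap the share, but they make shares of 20% or more hard to defend as the expected case. This limits the size of the problem.

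The third reply is that timing sub-analyses are already planned. They help, but they depend on feasibility and do not say which result is the headline.

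A reader might also argue that women first exposed late have necessarily stayed pregnant until then. That is true, but it bears mainly on spontaneous abortion and adds little for structural defects.

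**Conclusion.** The point holds as an inconsistency to be reconciled. The stated intention is first-trimester exposure, but the sections that build the primary comparison would let late-only exposures in.

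The effect is probably small. For late-only shares of 2% to 10%, restriction gains between 0 and about 5 points of Fisher power, and the expected relative risk in the any-time cohort falls from 3.8 to between 3.74 and 3.52. A large loss of power, such as 61.1% at a 20% share, needs a share that the protocol does not give and its enrolment pattern does not suggest. It should not be read as the expected case.

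All these sizes rest on two assumptions: the share itself, and RR 1 for late-only exposure. Under the second, any positive late-only share moves the relative risk toward 1. At the shares tried, restriction never loses power relative to the any-time set.

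**What to change.** In Section 9.7.2.5.1 and in the two major-defect rows of the Section 9.7.2.4.1 table, define the primary exposed set for major structural birth defects as Specific Evolocumab-Exposed pregnancies with at least one exposure between the first day of the LMP and the end of the first trimester, compared with Comparison Group I. State the gestational week that ends the first trimester for this purpose.

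Keep the any-time cohort for the other outcomes and as a sensitivity analysis of the primary outcome. Report late-only exposures separately.

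Add a note to Table 3 that the primary N of 71 is an upper bound for the number exposed in the first trimester. An exact replacement cannot be given, because the protocol has no figure for the late-only share.

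The cost is a few sentences. Timing of exposure is already a planned analysis variable, so no new data collection should be needed. The downside is slightly fewer exposed pregnancies in the headline analysis.
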